## 21 Monitoring

### 21.1 Trial management committee

This comparative effectiveness study involves the use of two opiate substitution medications that are Health Canada-approved for use in moderate- to severe-OUD. In addition, the study RAAM clinics are accredited facilities with trained personnel in the use of both study treatments for the treatment of moderate- to severe-OUD. As such, an informal trial management committee will be created to ensure that all privacy requirements for data collection, storage and dissemination are met. In addition, this committee will meet biannually to review data quality, including amount and reasons for missing data, and provide guidance to investigators on these issues.

An informal trial management committee will be created to ensure study recruitment and retention is optimized. The committee will be composed of members of the study RAAM clinics' administration and members of the Research Institute. The members of the committee will perform quarterly audits on a random sample of 5% of enrolled participants, and these audits will involve, but not be limited to, the following:

- (i) Documentation of consent and consistent application of inclusion and exclusion criteria
- (ii) Adherence to study treatment allocation
- (iii) Completeness and accuracy of the electronic case report forms
- (iv) Protocol deviations and reporting

This committee will submit quarterly reports to the data management committee as part of their responsibilities.

### 21.2 Interim analysis

There will be no interim analysis or premature termination of the study.

## 22 Harms

In this pragmatic, comparative effectiveness study, the RAAM clinic healthcare providers will document adverse events that occur during the study according to their clinical judgement and

usual standard of care. The subsequent clinical decisions and actions to any adverse event will be left up to the discretion of the healthcare providers. The only adverse event that will be considered serious will be any healthcare utilization for any reason during the 12-month study period, defined as any emergency room visit, admission to hospital, mental health facility or detoxification centre. Screening for these events will occur with each clinic visit by soliciting the information from the participant but will also occur unsolicited by screening the electronic health record system between visits. These healthcare utilization events will be reported to the Trial and Data management committees on a quarterly basis, along with the Research Ethics Board according to local regulatory standards.

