##### 4.32 Roles and responsibilities

###### 4.32a Trial sponsor

The trial sponsor has no role in the design, analyses, interpretation of the data, writing or decision to report the study results. The sponsor will support study coordination and execution, including informed consent, enrollment, randomization, follow-up, administering questionnaires, data collection and storage, and monitoring. The study sponsor is responsible for taking all reasonable steps to ensure proper conduct of the clinical trial protocol, and that the clinical trial is performed in accordance with the International Council for Harmonisation for Good Clinical Practice (<https://www.ich.org/page/efficacy-guidelines#6>) and all applicable regulatory requirements.

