##### *4.42b Roles and responsibilities*

Study planning  
Serious unexpected suspected adverse events reporting

Responsible for master file  
Site visits and monitoring  
Data quality and audit

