#### 18.11 Routinely collected data

##### *18.11a Prior to induction*

For all RAAM clinic patients with OUD who are eligible to receive any opiate substitution therapy, the following demographic and baseline clinical and laboratory data are collected **prior to induction** with any treatment (Table):

Data	Description	Data type
Demographics		
Date of birth	Month/day/year	Mm/dd/yyyy
Sex at birth	Male: Female	Categorical
Pregnant	Yes: No	Categorical
Ontario health insurance plan number	Unique provincial insurance number assigned to every resident	xxxx-xxx-xxx-version code
Ontario drug plan status	Insured versus non-insured	Categorical
Residency	Homeless; transient (< 6 months at same address, couch surfing or shelter); stable (≥ 6 months at same address)	Categorical
Children in home	Yes: No	Categorical
Children ages	Years	Continuous
Telephone contact	Yes: No	Categorical
Number		(xxx)-xxx-xxxx
Employment status 	Full-time (≥ 40 hours per week for ≥ 90 days per year); Part-time (≤ 40 hours per week or ≥ 90 days per year); Casual (≤ 90 days per year); unemployed	Categorical
Incarceration 	Incarceration in ≤ 12 months (Yes: No)	Categorical
Race 	White: Non-white, non-indigenous: Indigenous	Categorical
Clinical		
OUD diagnostic screen	≥ 2 of 11 DSM-V criteria must be present ≤ 12 months for diagnosis of OUD	Categorical: range 0 to 11:
OUD severity	DSM-V criteria of mild, moderate or severe OUD	Categorical: mild (2-3 criteria); moderate (4-5 criteria); severe (≥6 criteria)
Medical history	Comorbid illness screen, including mental health and substance use	Categorical
Medications	Prescribed	Categorical

Alcohol use	Yes: No	Categorical
Opioid use	Type: Route	Categorical
Other substance use	Type: Route	
Recent substance/opioid use	Timeline Followback questionnaire (assesses use and frequency of use of substances over the previous 7 days)	Categorical
Hospitalization	Substance-related $\leq$ 12 months (includes emergency room visit, admission to hospital, mental health or detoxification facility) (Yes: No)	Categorical
General physical exam	Vital signs; height; weight	Continuous
Opioid withdrawal screen	$\geq$ 3 of the following: dysphoria; nausea or vomiting; muscle aches; lacrimation or rhinorrhea; pupillary dilation or piloerection or sweating; diarrhea; fever; insomnia; yawning	Categorical; range 0-9
Jaundice	Yes: No	Categorical
Mental status	Glasgow coma scale	Categorical (range 3-15)

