#### 18.11b During treatment

Data	Description	Data type
------	-------------	-----------

Urine toxicology	Section 12.11a for description	Nominal
Recent substance/opioid use	Timeline Followback questionnaire (assesses use and frequency of use of substances over the previous 7 days)	Categorical
Counselling	Individual patient counselling for OUD, mental health and trauma	Narrative
General exam	Vital signs: Glasgow coma scale:	Continuous
Pregnancy	b-hCG assay (Yes: No)	Categorical
Bloodwork (optional)	Electrolytes: Liver: Renal	Continuous
Buprenorphine breakthrough dosing	Extra buprenorphine dosed for breakthrough	Continuous
Compliance	Missed appointments or doses (Yes: No)	Categorical
Hospitalization 	Any Royal Victoria Regional Health Centre emergency room visits, admissions to hospital or mental health or detoxification centre since previous clinic visit (Yes: No)	Categorical
Reason for visit/admission	Opioid-related (Yes: No)	Categorical
Serious adverse events 	Hospitalization (for any reason)	Categorical
Reason	Opioid-related (Yes: No)	Categorical

 Only hospitalization events associated with the Royal Victoria Regional Health Centre are accessible to the RAAM clinic healthcare providers as the clinics share the same electronic health record system as previously described. All other hospitalizations would have to be self-reported by the participants and consent for access to the health records would then need to be secured by the RAAM clinic healthcare providers.

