When a patient is enrolled and randomized, a unique study number will be automatically generated in REDCap. This unique study number, along with the patient's name (first, middle, last), Ontario Health Insurance Plan number, date of birth, and unique electronic health record system number will be stored in a password-protected EXCEL computer file. This study EXCEL file will be stored in a dedicated, password-protected electronic shared drive located on the Royal Victoria Regional Health Centre Personal Health Information Protection Act (PHIPA)-compliant servers. This EXCEL file will permit linkage to the electronic case report form to enable study personnel to record repeated measurements over the study period for a participant. Real-time data quality rules will be implemented in REDCap that will display warning pop-up messages whenever the rules are violated during data entry. These quality rules will minimize missing values in required fields; prevent incorrect data type entry and out of range data entry; identify outliers for numerical fields; and prevent invalid data entry into multiple choice fields. The data quality rules will also be available to be executed at any time by a study monitor or study personnel. All electronic case report form entries and edits are associated with an electronic audit trail that identifies the user, date and time of entry, and entry type. The type of activity that study personnel may undertake in REDCap is regulated by privileges associated with their user identification and password. Incremental data back-ups of REDCap are routinely performed twice a day, with off-site storage of the backed-up files done on a monthly basis. Data status reports on missing data will be provided to the Data management committee on a biweekly schedule for review. All study data will be archived in REDCap for 25 years and subsequently permanently destroyed.

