## 23 Auditing

### 23.1 Investigator responsibilities

The investigators agree to perform the clinical trial in accordance with this clinical trial protocol, International Council for Harmonisation guideline for Good Clinical Practice (<https://ichgcp.net/>) and all applicable regulatory requirements.

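### Section 22 limits serious adverse events to healthcare utilization, so a known death with no ER visit or admission is not classed as serious and need not be in the planned safety reports

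*Combined protocol and SAP*

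**What the plan says.** Section 22 (Harms) sets an exclusive rule: "The only adverse event that will be considered serious will be any healthcare utilization for any reason during the 12-month study period". The rest of that sentence lists what counts: an ER visit, or admission to hospital, a mental health facility or a detoxification centre. Death is not on the list. The reporting rule then says: "These healthcare utilization events will be reported to the Trial and Data management committees on a quarterly basis". The same sentence sends these events to the Research Ethics Board under local standards.

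The data tables follow the same line. In Section 18.11b and again in Section 18.12, the serious adverse event row reads "Hospitalization (for any reason", followed by a yes/no item on whether the reason was opioid-related. Neither table has a row for death.

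Section 4.42b gives the trial management committee the task "Serious unexpected suspected adverse events reporting", without saying what serious means.

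Death appears elsewhere as outcome data. Section 12.11 obtains dates of death by registry linkage for the relapse-free-weeks denominator. Section 12.24 makes opioid-attributable death a secondary outcome.

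**The concern.** The rule ranks events in an order that is hard to defend. Any ER visit known to the clinic, however minor, is serious and goes to the committees each quarter. A fatal overdose at home that the clinic also knows of is not serious under the same rule, and nothing requires it to be sent. The trial enrols people with moderate to severe opioid use disorder, and its own background and mortality sections stress the rise in opioid-related deaths.

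What is at stake is whether each known death is classified and passed on as a safety event while the trial runs. Detecting a mortality difference between arms is a separate matter, and this point does not rest on it.

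**Working it through.** No arithmetic applies. The check is to apply the rule as written to particular cases, then to look for any other provision that closes the gap.

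**Applying Section 22 and the serious-event rows**

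1. *Minor ER visit, participant discharged the same day.* It is on the Section 22 list, so it is serious and belongs in the quarterly reports.
2. *Death after admission.* The admission is on the list, so the event is serious. The rows record the hospitalization and whether it was opioid-related. They have no item for a fatal outcome.
3. *Death at home, known to the clinic, with no ER visit or admission.* Nothing on the list occurred. The event is not serious, has no serious-event field, and lies outside the reporting sentence.

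A broad reading of hospitalization does not help. The Section 18.11a history item uses the word in a way that "includes emergency room visit, admission to hospital, mental health or detoxification facility", and the hospitalization rows of Sections 18.11b and 18.12 are similarly wide. Even at that width, the word does not cover a death in the community.

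**Looking for another provision**

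- *Section 22, opening sentence.* Providers document adverse events by clinical judgement and usual care. A death could be recorded this way, but only as a non-serious event under the sentence that defines serious.
- *Section 24.* Safety and progress reports go to the ethics board at least annually and include the total number of adverse events. A death recorded by judgement could be counted there. Deaths are not named, and these reports do not go to the committees.
- *Section 4.42b.* The committee role uses the word serious, and Section 22 is the only place that defines it.
- *Section 13.* The schedule has a serious adverse event row with a case report form, but gives no definition.
- *Section 19.* "Data status reports on missing data will be provided to the Data management committee on a biweekly schedule for review". A participant who has died would appear there as missed data, not as a safety event.
- *Section 21.1.* The committee reviews reasons for missing data and audits a random 5% of participants each quarter. The audit list is open-ended but does not name deaths.
- *Section 23.4.* The monitor reviews adverse event documentation twice a year, against the protocol that contains the gap.
- *Sections 12.11 and 12.24.* Linkage and the mortality outcome serve the analysis. Neither is tied to safety reporting, and the mortality outcome covers opioid-attributable deaths only.

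Several of these routes could bring a death to light. None requires a known death to be classified and reported as a safety event during the trial.

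**Size**

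The expected number of deaths in the gap would be 90 × r × s × k. Here 90 is the target sample, r the 12-month risk of death, s the share of deaths without an ER visit or admission, and k the share of those that the clinic learns of during the trial. The documents give the 90 and none of the other three. The regional death counts in Section 5.12 describe a general population, not patients on treatment. The size therefore cannot be computed.

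**The case against.** The strongest reply has three parts.

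First, Section 22 says what will be reported and prohibits nothing. Section 21.1 provides further quarterly reports whose content is not limited, and providers may record any adverse event by judgement, which can then reach the ethics board under Section 24. This stands. A reader might infer that such deaths are barred from the quarterly reports, and the text does not support that. It supports only that they are not required.

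Second, the recipients may already know. Section 4.41a lists the investigators as members of the trial and data management committees, and Section 21.1 draws the management committee from clinic administration and the Research Institute. Section 21.2 rules out interim analysis and premature termination, so no stopping decision depends on the report. This lowers the practical stakes. It does not replace a written classification, because informal knowledge leaves no record in the safety data and does not reach the ethics board.

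Third, deaths are not lost to the trial. This also stands: dates come by linkage, and opioid-related mortality is analysed.

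A reader might also infer a conflict with the Good Clinical Practice commitments in Sections 4.32a and 23.1. The documents name that guideline but do not quote its definition of serious, so the conflict cannot be shown from them and the point does not use it.

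**Conclusion.** The concern holds as a gap in definition and reporting. Under Section 22 and the rows in Sections 18.11b and 18.12, a known death without an ER visit or admission is not classed as serious, has no serious-event field, and is not required in the quarterly committee reports or the ethics board reports that Section 22 sets up. This follows from the wording alone and rests on no numerical assumption.

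Its reach is limited. The primary analyses do not change, and mortality data remain available through Sections 12.11 and 12.24. A reader might want to attach a probability that at least one such death occurs. That would need a death risk, an out-of-hospital share and a share known to the clinic, all absent from the documents, so any figure would reflect the chosen inputs. The point should be fixed because the rule is wrong as written and the correction is cheap.

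**What to change.** - In Section 22 and the serious adverse event rows of Sections 18.11b and 18.12, add death from any cause, in or out of hospital, as a serious adverse event, with fields for date and for cause where known.
- Include each known death in the quarterly committee reports and the ethics board reports already planned. A breakdown by arm is not needed to cure the defect.
- Reconcile Section 22 with the committee's reporting role in Section 4.42b, so that serious has one meaning in both places.

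The cost is protocol wording and a few form fields, with no new visit, test or tracing procedure. Some deaths will still be learned of only through registry linkage. The change makes known deaths reportable and does not promise that every death is found during the trial.

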## 12 Outcomes

### 12.1 Primary outcome measures

#### 12.11 Opioid positivity

Difference in proportions of relapse-free weeks (RFWs) at 12-months from the date of randomization, where ***relapse-free weeks are defined by the cumulative number of weeks alive during the study period in which there was a negative urine drug screen and negative self-report for non-prescribed opioids.*** The potential number of RFWs for each patient is the cumulative number of weeks that the patient is alive during the 12-month study period, with a maximum of 48 weeks. A week is defined as a consecutive 7-day period starting on the day of the week that randomization occurred. A patient is considered to have 'completed' a week as long as they are alive for  $\geq 1$  day of that week. For example, if a patient is randomized on a Tuesday, and subsequently dies on a Thursday of the 32nd week, the patient will have been considered to have been alive for 32 weeks. The denominator used in estimating the proportion of RFWs will be the total number of weeks that the patient was alive during the study period. Vital statistics for all participants (date and year of death) will be available through linkage with the Office of the Registrar General of Ontario database. The cumulative number of RFWs alive will be used as the numerator in estimating the proportion of RFWs. Scheduled urine drug testing and self-reports will occur every 2 weeks during the study period starting in week 2 from randomization. Imputation of missing data will occur for those weeks in which a urine drug screen/self-report was not scheduled according to the results of the subsequent week's urine drug screen/self-report. For example, if a urine drug screen/self-report was not scheduled for week 11, but a scheduled urine drug screen/self-report was done on week 12 and week 12 met the criteria for a RFW, then week 11 would be imputed as a RFW (Figure 1). Similarly, for weeks with scheduled urine drug screen/self-reports that are missed, that week and the preceding week in which there was no scheduled urine drug screen/self-report will not be counted as RFWs (for example, see Figure 1, week 17 and 18). In the hypothetical patient represented in Figure 1, 20 urine drug screens/self-reports were completed, with 5 positive and 15 negative urine drug screens/self-reports, resulting in 30 cumulative RFWs over the 48-week study period, or a proportion of RFWs of 0.625.

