### 12.24 Mortality

Difference in mortality proportions, where **mortality is defined as any death attributable to opioid use regardless of the intent**. Opioid-related deaths continue to increase year after year and have emerged as a public health crisis. Only 2 previous opiate substitution treatment studies measured mortality as an outcome, the latest published in 1980. The method used by the Canadian Institute for Health Information will be used to measure mortality in this study given its validity, reproducibility, importance to both healthcare providers and patients with OUD, and its responsiveness to opiate substitution therapies.

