## 20.12 Secondary outcomes

We will use a 3-level hierarchical design to model all the repeated measures outcomes (Medications Satisfaction Questionnaire and the WHOQOL-BREF) where the outcomes will be coded as continuous. Level 1 observations are clustered within individual participants (Level 2), which are nested within RAAM clinic sites (Level 3). We will analyse the data using multi-level, mixed-effects linear regression analysis with random effects estimated for the variance in the

intercepts of both participant and clinic levels. We will include a random slope on the indicator for OUD severity (moderate versus severe) in the Level 2 random effects equation using an unstructured covariance structure between intercept and slope. We will also include clinic visit and an interaction term between clinic visit and treatment, along with any baseline demographic or clinical variables that are unbalanced at Level 1.

Both clinic retention and mortality will be coded as binary outcomes. We will conduct unadjusted analyses for both using a chi-squared test (with continuity correction) or Fisher's exact test depending on cell sizes.

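### Section 22's definition of a serious adverse event leaves out a death or life-threatening event that involves no emergency visit or admission

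*Combined protocol and SAP*

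**What the plan says.** Section 22 leaves adverse event documentation to the providers' judgement and then defines seriousness in one sentence: "The only adverse event that will be considered serious will be any healthcare utilization for any reason during the 12-month study period", which is "defined as any emergency room visit, admission to hospital, mental health facility or detoxification centre". The reporting sentence refers back to the same events: "These healthcare utilization events will be reported to the Trial and Data management committees on a quarterly basis". It adds the ethics board, with timing set by local regulatory standards. Detection is by asking the participant at each visit and by screening the electronic record between visits.

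The data tables in 18.11b and 18.12 carry a serious adverse event row described as hospitalization from any cause, with one reason item, a yes/no on whether the event was opioid-related. The timeline in section 13 marks the serious event item as a case report form entry completed by the provider. That form is not reproduced.

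Death appears elsewhere as outcome data. In 12.11, "Vital statistics for all participants (date and year of death) will be available through linkage", and the number of weeks alive is the denominator of the first primary outcome. In 12.12 days alive play the same part for the second. In 12.24, "mortality is defined as any death attributable to opioid use regardless of the intent". Section 20.12 gives its analysis: "Both clinic retention and mortality will be coded as binary outcomes", compared by a chi-squared or Fisher's exact test.

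Section 4.42b lists, among the trial management committee's duties, "Serious unexpected suspected adverse events reporting".

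**The concern.** A definition of seriousness decides which events are escalated. This one uses contact with a facility as the sole criterion and excludes everything else by the word *only*. Two kinds of event fall outside it: a death with no emergency visit or admission, and a life-threatening event, such as an overdose reversed in the community, with none. In opioid use disorder these are plausible, and they are the events that safety oversight most needs to see.

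Section 21.2 rules out interim analysis and premature termination, so event reporting carries most of the safety oversight. The concern is the protection of participants and the accuracy of the safety record. It is not the validity of the treatment comparison.

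**Working it through.** No arithmetic applies. The check is to run specific events through section 22 as written and then look for any other text that brings the excluded ones back in.

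| Event during the 12 months | Serious under section 22? | In section 22 reports? | Where else it is captured |
|---|---|---|---|
| Admission to a detoxification centre | Yes | Yes | Hospitalization rows, 18.11b and 18.12 |
| Overdose death in an emergency room or on a ward | Yes, through the visit or admission | Yes | Primary outcome denominators; mortality outcome |
| Overdose death at home, no facility contact | No | No | Primary outcome denominators; mortality outcome; adverse event if charted |
| Death from a non-opioid cause, no facility contact | No | No | Primary outcome denominators; adverse event if charted |
| Life-threatening overdose reversed in the community | No | No | Adverse event if charted; possibly a positive urine screen or self-report |

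So a detoxification stay counts as serious and a death at home does not.

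Could other text widen the definition?

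1. *The reporting sentence in section 22.* Its subject is the healthcare utilization events, so the reference to local regulatory standards sets the timing for those events and adds no others.
2. *Mortality outcome (12.24, 20.12).* This is an end-of-study comparison restricted to opioid-attributable deaths. It is not a reporting route.
3. *Registry death dates (12.11).* They cover deaths from any cause, but serve the denominators. No timing is given for the linkage, and nothing ties it to safety reporting.
4. *Monitor and ethics board (23.4, 24).* The monitor reviews adverse event documentation, and the board receives adverse event totals at least annually. A charted death would be visible there, but not as a serious event.
5. *Good Clinical Practice commitments (4.32a, 23.1).* These are general. They do not restate or amend the section 22 definition.

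No section adds death or life-threatening events to the definition.

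Detection has a related weakness. A participant who has died cannot be asked at a visit. The footnotes to 18.11b and 18.12 say that only the sponsor hospital's own hospitalization events are visible to the clinics, with others depending on self-report. Section 22 does not make loss of contact a reason to check vital status.

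**The case against.** The strongest reply is that this is a low-intervention trial of two approved drugs used within their authorization (section 26), in accredited clinics with trained staff (21.1), so a light safety scheme is proportionate. That supports light causality grading. It gives no reason to leave death out of the definition.

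A second reply is that investigators are bound to the protocol, Good Clinical Practice and all applicable regulatory requirements together (23.1), so a death would be reported anyway. It might be. But the documents do not say which prevails when a general commitment meets a specific contrary rule, and staff following section 22 would be right to class the death as not serious.

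Three stronger readings are tempting, and the documents do not support them:

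- *That the trial would not record these deaths.* Every death affects the denominators of both primary outcomes, opioid-attributable deaths are a secondary outcome, and providers may chart any death. The gap is in classification and reporting.
- *That relatedness and expectedness are recorded nowhere.* 18.11b and 18.12 are summary tables, and the serious-event form marked in section 13 is not shown. Urine results, self-reports, breakthrough dosing and missed doses are also collected and would inform attribution. What can be said is that the one listed reason item does not by itself supply the two judgements that the 4.42b duty needs. Both drugs contain an opioid, so a yes does not alone distinguish the effect of the study drug from relapse.
- *That linked death records could never feed a safety report because the research data must stay in the secure environment of 18.13.* The list in 18.13 does not name the Registrar General database, so whether that restriction applies to death dates is not stated.

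**Conclusion.** The point holds. Section 22 is wrong as written: it classifies a death or life-threatening event without an emergency visit or admission as not serious, which leaves it outside that section's reports to the committees and the ethics board. No other text corrects this.

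Its size cannot be given as a number of events, because the documents contain no death rate or drug-related event rate for treated patients. The effect on the planned analyses is nil. The case for change rests on participant safety and a low cost, and the text should be corrected.

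The conclusion assumes that the limiting words in section 22 mean what they say and that no document outside this set, such as a serious-event form or operating procedure, widens the definition. Confidence is high for the definition. It is lower for the relatedness and expectedness items, which are offered as an option.

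**What to change.** 1. In section 22, define as serious any death or life-threatening event, with or without healthcare contact, in addition to the healthcare utilization already listed. Extend the reporting sentence to cover these events.
2. In 18.11b and 18.12, replace the all-cause hospitalization entry in the serious adverse event row with four listed categories: death, life-threatening event, emergency room visit, admission. Without this, a death would be serious by definition but have no listed item.
3. Treat a missed visit followed by failed contact as a prompt to check vital status. The pre-visit calls already planned in 11.5 and 18.21 supply the contact attempt.

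The cost is a few sentences, a revised data row and a little coordinator time. No new committee or staff are needed. One limit remains: a death after withdrawal may still be found only by registry linkage.

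Optional: for each serious event, have the provider record whether it was related to the allocated drug and whether it was expected, so that the committee has direct input for its 4.42b duty. If the unseen form already does this, nothing is needed. The drawback is that providers know the allocation and may attribute events differently by arm.
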